Statistical Methods	
Efficacy analysis
 
The primary analysis of OS will be conducted in the ITT population (all randomized subjects) using a stratified (by the randomization stratification factors) logrank test at the two-sided alpha=0.05 level of significance.
 
If the primary analysis of OS is statistically significant, then the key secondary endpoints of PFS and ORR will be analyzed using a fixed-sequence testing procedure. First, PFS will be analyzed using the same statistical methods that are used in the primary efficacy analysis of OS.
 
If the analysis of PFS is statistically significant, then ORR will be analyzed using the Cochran-Mantel-Haenszel test stratified by the randomization stratification factors. However, if a prior test is not statistically significant, then the subsequent analyses will be exploratory rather than confirmatory.
 
All other secondary efficacy endpoints will be analyzed using two-sided tests at the alpha=0.05 level of significance, with no adjustments for multiplicity DCR will be analyzed using the same methodology as described for ORR.
 
For the European Organization for Research and Treatment of Cancer Quality of Life Questionnaire-Core 30 (EORTC QLQ-C30) and EuroQol 5-Dimension 5-Level (EQ-5D-5L) Questionnaire, the treatment groups will be compared using analysis of covariance (ANCOVA) models with treatment group and the randomization stratification variables as factors, and with the baseline value of the corresponding endpoint as a covariate.
 
Safety analysis
 
Safety parameter data will be summarized and listed by patient. Summary tables will show incidence rates (number of subjects with at least one event) of AE, SAE, etc., as well as summaries of severity (CTCAE v4.03) and causal relationship. Change from baseline tables will be presented for clinical laboratory assessments, vital signs and ECOG performance score. Laboratory abnormalities will also be

	summarized in tables showing shifts in grade.

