**Table 3. Noncompartmental Mean Pharmacokinetic Parameters of YN968D1 after Single or Multiple Oral Doses**

PK Parameter	Single Oral Dose			Multiple Oral Dose of 750 mg			
	500 mg (n=8)	750 mg (n=12)	850 mg (n=8)	Day 1 (n=11)	Day 6 (n=11)	Day 28 (n=11)	Day 56 (n=11)
$C_{max}$ ng/mL	1,521	2,379	2,833	2,421	2,553	2,210	1,854
(%CV)	(75.1)	(55.9)	(90.0)	(68.5)	(52.8)	(45.5)	(51.2)
$t_{max}$ hour (range)	3.5 (3.0-8.0)	3.0 (2.0-4.0)	4.0 (1.5-8.0)	3.0 (2.0-8.0)	4.0 (3.0-8.0)	4.0 (2.0-6.0)	3.0 (2.0-6.0)

PK Parameter	Single Oral Dose			Multiple Oral Dose of 750 mg			
	500 mg (n=8)	750 mg (n=12)	850 mg (n=8)	Day 1 (n=11)	Day 6 (n=11)	Day 28 (n=11)	Day 56 (n=11)
AUC 0-24 ng.hr/mL (%CV)	11,295 (68.7)	18,172 (59.3)	21,975 (80.8)	19,399 (60.5)	25,449 (59.2)	19,946 (43.2)	15,629 (63.2)
t 1/2λz hours (%CV)	8.1 (30.7)	9.0 (15.1)	9.1 (33.1)	8.9 (25.8)	11.0 (56.7)	11.3 (66.5)	8.3 (61.0)

Abbreviations: Cmax, maximum plasma concentration; CV, coefficient of variation; tmax, time to reach Cmax; AUC0-24, area under plasma concentration-time curve; t1/2λz, half-life associate with terminal slope of a semilogarithmic concentration-time curve

The safety population comprised all subjects who had received at least 1 dose of YN968D1 (N=46). The most frequently observed adverse drug reactions were hypertension (69.5%, 29 grade 1-2 and 3 grade 3-4), proteinuria (47.8%, 16 grade 1-2 and 6 grade 3-4), and hand-foot syndrome (45.6%, 15 grade 1-2 and 6 grade 3-4). Hypertension was generally manageable with antihypertensive agents. Approximately 10 % of the subjects who developed HFS progressed to Grade 3. Other treatment-related AEs were generally mild or moderate in severity and were manageable. The treatment was discontinued for both of the two subjects who experienced DLT. After recovery, one (1) subject was able to reinitiate treatment at a reduced dose. A total of 15 subjects received at least one cycle of YN968D1 at the initial dose. Four (4) subjects discontinued the treatment during Cycle 1, of which 1 subject in the 250 mg dose group due to disease progression and 3 in the 1,000 mg dose group due to intolerable toxicity. Eighteen (18) subjects had a dose reduction for different toxicities during the extended treatment (1 in 1,000 mg group, 13 in 850 mg group, and 4 in 750 mg group). For those subjects who experienced dose reduction, the mean duration of treatment with YN968D1 was 5.4 months.

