8.2.1 Overall Summary of Adverse Events

The number of subjects, incidence rate with its 95% CI and number of events will be presented for TEAEs, adverse drug reaction (ADR) and serious adverse event by treatment group during the study. Chi-square test or Fisher's exact test will be used for comparison of AE incidence between groups.

Data will be summarized in the following tables.

- *Table. Overall Summary of TEAEs – Safety Set*

- *Table. Overall Summary of Serious TEAEs – Safety Set*

- *Table. Overall Summary of ADRs – Safety Set*

- *Table. Overall Summary of Serious ADRs – Safety Set*

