8.2.2 Display of Adverse Events

All TEAEs and ADR will be presented according to standardized SOC and PT. The following conventions will be used in summarizing AEs:

- For subject incidence summaries, a subject will be counted only once within each SOC and within each PT.
- Summaries by NCI-CTCAE grade – if a subject reports more than 1 AE within an SOC and/or PT, the AE with the highest severity within each SOC and within each PT will be included.
- When the number of events is calculated, more than 1 AE counted as different events

Data will be summarized in the following tables and listings.

- *Table. Incidence of TEAEs by SOC and PT – Safety Set*
- *Table. Incidence of ADRs by SOC and PT – Safety Set*
- *Table. Incidence of TEAEs by the Worst NCI-CTC Grade, SOC and PT [Rivoceranib + BSC] – Safety Set*
- *Table. Incidence of TEAEs by the Worst NCI-CTC Grade, SOC and PT [Placebo + BSC] – Safety Set*
- *Table. Number of TEAEs by NCI-CTCAE, SOC and PT [Rivoceranib + BSC] – Safety Set*
- *Table. Number of TEAEs by NCI-CTCAE, SOC and PT [Placebo + BSC] – Safety Set*
- *Table. Incidence of ADRs by the Worst NCI-CTC Grade, SOC and PT [Rivoceranib + BSC] – Safety Set*
- *Table. Incidence of ADRs by the Worst NCI-CTC Grade, SOC and PT [Placebo + BSC] – Safety Set*
- *Table. Number of ADRs by NCI-CTCAE, SOC and PT [Rivoceranib + BSC] – Safety Set*
- *Table. Number of ADRs by NCI-CTCAE, SOC and PT [Placebo + BSC] – Safety Set*
- *List. Subjects with TEAEs – Safety Set*

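### SAP 8.2.1 compares the arms only on ungraded adverse-event incidence, so the body of the SAP plans no between-arm estimate of Grade ≥3 toxicity

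*SAP*

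**What the plan says.** SAP 8.2.1 gives subject counts, incidence with 95% CI and event counts. These "will be presented for TEAEs, adverse drug reaction (ADR) and serious adverse event by treatment group during the study". Four overall tables follow: TEAEs, serious TEAEs, ADRs and serious ADRs. A chi-square or Fisher test "will be used for comparison of AE incidence between groups". Neither the text nor the table titles mention grade.

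Grade enters in SAP 8.2.2. When a subject has several events, "the AE with the highest severity within each SOC and within each PT will be included". The output is split by arm: one table is titled "Incidence of TEAEs by the Worst NCI-CTC Grade, SOC and PT [Rivoceranib + BSC" and its twin "Incidence of TEAEs by the Worst NCI-CTC Grade, SOC and PT [Placebo + BSC". The ADR tables are split in the same way. No test, difference or overall Grade ≥3 row is named.

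SAP 8.2.3 tabulates, by arm and without a test, serious events, fatal events, and events that led to stopping, reducing or interrupting the drug. SAP 10.4 is a general rule for categorical data and adds no graded contrast. On severity, the protocol synopsis promises incidence rates "as well as summaries of severity (CTCAE v4.03) and causal relationship". It promises no test.

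**The concern.** The drug's known toxicities have a substantial severe component. The phase I results in Protocol 1.2 list "hand-foot syndrome (45.6%, 15 grade 1-2 and 6 grade 3-4" among 46 subjects, with 6 Grade 3–4 cases of proteinuria and 3 of hypertension. An ungraded comparison cannot show a shift from Grade 1–2 to Grade 3.

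If nearly all subjects in both arms report some event, the any-TEAE row also has little room to differ. The summary could then show no significant difference in TEAEs while severe toxicity is more frequent on the drug. The reader would have to judge that from two separate tables.

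**Working it through.** **Is the Grade ≥3 figure recoverable from the planned tables?** No. SAP 8.2.2 takes the worst grade within each SOC and each PT, so a subject with Grade 3 hypertension and Grade 3 hand-foot syndrome appears in two rows. The phase I counts show the size of the ambiguity. Grade 3–4 counts of 6, 6 and 3 out of 46 fit anything from 6/46 = 13% of subjects (complete overlap) to 15/46 = 33% (no overlap).

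**Do the other rows cover it?**
- *Serious events.* SAP 5.9.3 lists death, threat to life, inpatient hospitalization, disability and congenital anomaly, and has no criterion for otherwise important medical events. A Grade 3 event managed without admission or lasting disability is not serious under that list.
- *ADRs.* Grade 1 and Grade 3 count alike. The definition also conflicts. SAP 5.9.4 counts all six causality terms of Protocol Table 7, including unlikely, so every event with a causality assessment is an ADR and the ADR row nearly repeats the TEAE row. SAP 8.2 omits unlikely, which agrees with Protocol 7.2.2.

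**Power.** Neither document states an AE rate or AE power for this trial, so there is no safety figure to reproduce. The one reproducible design figure is for OS: (1.960 + 0.842)² / [(2/3)(1/3)(ln 0.72)²] ≈ 328 events against 325 stated. That agrees with the 2:1 allocation and two-sided 5% level used below.

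Inputs:
- 459 subjects at 2:1 gives 306 v 153 if all are dosed.
- Tests follow SAP 10.4 (chi-square, or Fisher when sparse).
- Placebo rates are assumed.
- The drug effect is added independently to the placebo rate p: drug rate = 1 − (1 − p)(1 − e).
- For any TEAE, e = 32/46 = 0.696 (phase I hypertension).
- For Grade ≥3, e = 6/46 = 0.13 (one toxicity), or e = 1 − (40/46)²(43/46) = 0.29 (three toxicities treated as independent).

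| Comparison | Placebo | Drug | Power |
|---|---|---|---|
| Any TEAE | 98% | 99.4% | 26% |
| Any TEAE | 95% | 98.5% | 55% |
| Any TEAE | 90% | 97.0% | 86% |
| Grade ≥3, e = 0.29 | 30% | 50.5% | 99% |
| Grade ≥3, e = 0.29 | 40% | 57.6% | 95% |
| Grade ≥3, e = 0.29 | 50% | 64.7% | 85% |
| Grade ≥3, e = 0.13 | 30% | 39.1% | 49% |
| Grade ≥3, e = 0.13 | 40% | 47.8% | 36% |
| Grade ≥3, e = 0.13 | 50% | 56.5% | 26% |

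These powers are by exact enumeration. Simulation with 2,000 replicates agrees within its error and puts the last two at 35% and 25%.

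Applying e = 0.696 to any ADR gives about 100% power for placebo ADR rates of 20% to 70%, 99% at 80% and 86% at 90%.

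**Precision of the missing estimate.** For 60% v 40% with Grade ≥3, the 95% half-width of the risk difference is 1.96 × √(0.6 × 0.4/306 + 0.4 × 0.6/153) = 9.5 percentage points. The trial can estimate a severe-toxicity difference to within about 10 points.

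**The case against.** A reader might infer that severe non-serious toxicity is never set against placebo. The documents do not support that. SAP 8.2.2 plans matching worst-grade tables for both arms, and SAP 8.2.3 tabulates events that led to a reduced, interrupted or stopped dose. Protocol 4.4 has treatment withheld for related Grade III–IV toxicity, so much of the signal should surface there. This stands, but those tables are descriptive, depend on the causality call, and mix in dose reductions for Grade II events.

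A reader might also take the any-TEAE rate to be near 100% in both arms. Neither document gives that rate, or any placebo AE rate. At a 90% placebo rate the planned test is adequate on the model above. The any-ADR test could also show a clear difference where any TEAE does not, provided that the definition in SAP 8.2 applies.

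Nor is a graded test always more powerful. If the drug alone causes Grade ≥3 events in only 13% of subjects, the Grade ≥3 comparison has low power. A Wilcoxon test on worst grade can then be about 40 points weaker than the planned any-TEAE test at a 90% background.

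The protocol promises summaries of severity, and the SAP delivers them, so there is no breach. The mock-up tables in SAP Appendix 1.1 are not available and might contain a Grade ≥3 row. None of this supplies the between-arm estimate that the SAP text leaves out.

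**Conclusion.** The point holds as a gap in estimation. The SAP text plans no between-arm figure for subjects with any Grade ≥3 event, the tables by SOC and PT cannot yield one, and the serious-event and ADR rows do not replace it. This conclusion needs no assumption about background rates. It is subject only to the unseen mock-ups.

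The weakness of the any-TEAE test is conditional on a placebo rate above roughly 90%. The power figures rest on assumed placebo rates and on a single-arm phase I study of 46 subjects at several dose levels, with effects added independently. They indicate a range and do not predict the trial's results. The change is worth making because it estimates severe toxicity directly, not because it guarantees a more sensitive test.

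**What to change.** - In SAP 8.2.1, add side by side by arm: subjects with any Grade ≥3 TEAE and subjects with any Grade ≥3 ADR, each with the between-arm risk difference and 95% CI. Add the distribution of subjects by worst grade (none, 1 to 5). Keep the planned ungraded rows.
- In SAP 8.2.2, show both arms in one worst-grade table.
- Reconcile the ADR definitions in SAP 5.9.4 and 8.2, because every ADR row depends on which one applies.
- A Wilcoxon test on worst grade is optional.

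Cost: SAP wording and a few table rows from data already graded. The downside is one or two more unadjusted safety comparisons.

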8.2.2 Display of Adverse Events

All TEAEs and ADR will be presented according to standardized SOC and PT. The following conventions will be used in summarizing AEs:

- For subject incidence summaries, a subject will be counted only once within each SOC and within each PT.
- Summaries by NCI-CTCAE grade – if a subject reports more than 1 AE within an SOC and/or PT, the AE with the highest severity within each SOC and within each PT will be included.
- When the number of events is calculated, more than 1 AE counted as different events

Data will be summarized in the following tables and listings.

- *Table. Incidence of TEAEs by SOC and PT – Safety Set*
- *Table. Incidence of ADRs by SOC and PT – Safety Set*
- *Table. Incidence of TEAEs by the Worst NCI-CTC Grade, SOC and PT [Rivoceranib + BSC] – Safety Set*
- *Table. Incidence of TEAEs by the Worst NCI-CTC Grade, SOC and PT [Placebo + BSC] – Safety Set*
- *Table. Number of TEAEs by NCI-CTCAE, SOC and PT [Rivoceranib + BSC] – Safety Set*
- *Table. Number of TEAEs by NCI-CTCAE, SOC and PT [Placebo + BSC] – Safety Set*
- *Table. Incidence of ADRs by the Worst NCI-CTC Grade, SOC and PT [Rivoceranib + BSC] – Safety Set*
- *Table. Incidence of ADRs by the Worst NCI-CTC Grade, SOC and PT [Placebo + BSC] – Safety Set*
- *Table. Number of ADRs by NCI-CTCAE, SOC and PT [Rivoceranib + BSC] – Safety Set*
- *Table. Number of ADRs by NCI-CTCAE, SOC and PT [Placebo + BSC] – Safety Set*
- *List. Subjects with TEAEs – Safety Set*

8.2.3 Death and Serious Adverse Events and Other Significant Adverse Events

For Serious adverse events (SAEs, Sec 5.6.3), AEs leading to IP discontinuation and AEs leading to death, separate listings and summaries of subject counts and percents together with the number of events will be presented by treatment group and by SOC and PT. Also, subjects who died and primary reason of death will be summarized with counts and percents by treatment group.

Data will be summarized in the following tables and lists.

- *Table. Incidence of Serious TEAEs by SOC and PT – Safety Set*
- *Table. Incidence of Serious ADRs by SOC and PT – Safety Set*
- *Table. Incidence of TEAEs Leading to IP Discontinuation by SOC and PT – Safety Set*
- *Table. Incidence of ADRs Leading to IP Discontinuation by SOC and PT – Safety Set*
- *Table. Incidence of TEAEs Leading to IP Dose Reduction/Interruption by SOC and PT – Safety Set*
- *Table. Incidence of ADRs Leading to IP Dose Reduction/Interruption by SOC and PT – Safety Set*
- *Table. Incidence of TEAEs Leading to Fatal Outcome by SOC and PT – Safety Set*
- *Table. Incidence of ADRs Leading to Fatal Outcome by SOC and PT – Safety Set*
- *Table. Death Summary – Safety Set- List. Subjects with Serious TEAEs – Safety Set*
- *List. Subjects with Serious TEAEs – Safety Set*
- *List. Subjects with TEAEs Leading to IP Discontinuation – Safety Set*
- *List. Subjects with TEAEs Leading to IP Dose Reduction/Interruption – Safety Set*
- *List. Subjects with TEAEs Leading to Fatal – Safety Set*

8.2.4 Dose Limiting Toxicity (DLT)

Dose Limiting Toxicity data (Sec 5.6.5) will be collected only for the subjects enrolled in Japan Run-in. The incidence of DLT will be summarized and relevant subjects will be listed.

- *Table. Incidence of DLT in Japan Run-in – Safety Set*
- *List. Subjects with DLT in Japan Run-in – Safety Set*

8.3 Clinical Laboratory Evaluation

Laboratory data will be classified according to CTC Grade (NCI-CTCAE version 4.03). A shift table from baseline to worst NCI-CTC grade will be presented.

- *Table. Shift from Baseline of Hematology Tests by Worst NCI-CTC Grade: Rivoceranib + BSC [Parameter] – Safety Set*
- *Table. Shift from Baseline of Hematology Tests by Worst NCI-CTC Grade: Placebo + BSC [Parameter] – Safety Set*
- *Table. Shift from Baseline of Blood Chemistry Tests – serum electrolyte by Worst NCI-CTC Grade: Rivoceranib + BSC [Parameter] – Safety Set*
- *Table. Shift from Baseline of Blood Chemistry Tests – serum electrolyte by Worst NCI-CTC Grade: Placebo + BSC [Parameter] – Safety Set*
- *Table. Shift from Baseline of Blood Chemistry Tests – liver enzymes by Worst NCI-CTC Grade: Rivoceranib + BSC [Parameter] – Safety Set*
- *Table. Shift from Baseline of Blood Chemistry Tests – liver enzymes by Worst NCI-CTC Grade: Placebo + BSC [Parameter] – Safety Set*
- *Table. Shift from Baseline of Blood Chemistry Tests – others by Worst NCI-CTC Grade: Rivoceranib + BSC [Parameter] – Safety Set*
- *Table. Shift from Baseline of Blood Chemistry Tests – others by Worst NCI-CTC Grade: Placebo + BSC [Parameter] – Safety Set*

- *Table. Shift from Baseline of Coagulation Tests by Worst NCI-CTC Grade: Rivoceranib + BSC [Parameter] – Safety Set*
- *Table. Shift from Baseline of Coagulation Tests by Worst NCI-CTC Grade: Placebo + BSC [Parameter] – Safety Set*

To investigate a normal/abnormal shift from baseline by visit, results will be classified as Normal, Abnormal NCS, or Abnormal CS and presented with a shift table. Subjects who were 'Normal' or 'Abnormal - not clinically significant (NCS)' at baseline but shifted to 'Abnormal - clinically significant (CS)' will be summarized in the following tables and listings. Significant shift from baseline will be tested using McNemar's or Bowker's test.

- *Table. Shift from Baseline of Hematology Tests [Parameter] – Safety Set*
- *Table. Shift from Baseline of Blood Chemistry Tests – serum electrolyte [Parameter] – Safety Set*
- *Table. Shift from Baseline of Blood Chemistry Tests – liver enzymes [Parameter] – Safety Set*
- *Table. Shift from Baseline of Blood Chemistry Tests – others [Parameter] – Safety Set*

- *Table. Shift from Baseline of Coagulation Tests [Parameter] – Safety Set*

- *Table. Shift from Baseline of Urinalysis Tests [Parameter] – Safety Set*
- *List. Listing of individual laboratory measurements – Safety Set*
- *List. Subjects Shifting from Normal or NCS at Baseline to CS at Post-treatment on Laboratory – Safety Set*

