#### **Other safety endpoints including laboratory test results and vital signs**

For the analysis of safety data, including laboratory values, vital signs, physical examination, 12-lead ECG and ECOG performance status, continuous variables will be summarized using descriptive statistics (mean, median, SD, minimum and maximum) and categorical variables will be summarized using numbers and percentages of subjects. If it is necessary, a normal/abnormal shift of the safety endpoint will be summarized.

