8.5 Other Safety Measures

8.5.1 Vital Signs

Vital Sign parameters (Systolic Blood Pressure, Diastolic Blood Pressure, Pulse, Body Temperature, Respiratory Rate, and Weight) and the change from baseline at each scheduled visit will be summarized with descriptive statistics by visit and treatment group.

Data will be summarized in the following table.

- *Table. Vital Signs [Parameter] – Safety Set*

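### SAP 8.3 summarises laboratory data only by category and omits, without declaring it, the change-from-baseline and descriptive laboratory tables that the protocol promises

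*SAP*

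**What the plan says.** **Protocol.** The safety paragraph of the synopsis (Statistical Methods) states: "Change from baseline tables will be presented for clinical laboratory assessments, vital signs and ECOG performance score". It then adds that laboratory abnormalities will also be "summarized in tables showing shifts in grade". Protocol 8.3.7 says that for safety data "including laboratory values, vital signs, physical examination, 12-lead ECG and ECOG performance status, continuous variables will be summarized using descriptive statistics", and it names the mean, median, SD and range as those statistics. The same paragraph makes a normal/abnormal shift summary conditional on its being needed.

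**SAP.** Section 8.3 opens: "Laboratory data will be classified according to CTC Grade (NCI-CTCAE version 4.03). A shift table from baseline to worst NCI-CTC grade will be presented". It then plans a second family of tables that classify each result as Normal, Abnormal NCS or Abnormal CS and show the shift from baseline by visit, tested with McNemar's or Bowker's test. The section ends with two listings: individual laboratory measurements, and subjects who move to Abnormal CS. For vital signs, by contrast, SAP 8.5.1 plans the parameters "and the change from baseline at each scheduled visit will be summarized with descriptive statistics". SAP 8.5.3 does the same for ECG intervals.

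**The concern.** The two displays that the protocol treats as supplementary, the grade shift and the normal/abnormal shift, have become the whole laboratory summary. The numeric display that the protocol puts first is gone.

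A shift table records only movement across a boundary. If platelets fall or creatinine rises in one arm but the values stay in the same grade or category, every such subject sits on the diagonal of the table. The arms then look alike in the summary, whatever the size of the drift. A table of values and change by visit and arm would let a reader see it.

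Urine protein deserves separate mention. Proteinuria is one of the drug's established reactions, yet urinalysis gets only the Normal/NCS/CS display.

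**Working it through.** No laboratory figure in the plan needs recomputing. The check sets the documents side by side and counts the planned outputs.

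**1. Promised and planned**

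| Output | Protocol | SAP |
|---|---|---|
| Laboratory change from baseline | Synopsis: yes | 8.3: none named |
| Descriptive statistics for continuous laboratory values | 8.3.7: yes | 8.3: none named |
| Laboratory grade shifts | Synopsis: in addition | 8.3: yes |
| Normal/abnormal shifts | 8.3.7: if needed | 8.3: yes, in three levels |
| Vital signs, change from baseline | Synopsis: yes | 8.5.1: yes |
| ECG, descriptive statistics | 8.3.7: yes | 8.5.3: yes, with change from baseline |

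**2. Count of SAP 8.3 outputs**

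- Worst-grade shift tables: 5 test groups (hematology, three chemistry groups, coagulation) × 2 arms = 10.
- Normal/NCS/CS shift tables: the same 5 groups plus urinalysis = 6.
- Shift tables in total: 10 + 6 = 16.
- Tables of laboratory values or change from baseline: 0.
- Listings: 2, of which one gives the individual measurements.

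**3. Does another SAP section supply the missing tables?** SAP 10.2 says which statistics to show for a continuous variable. SAP 10.3 sets decimals for laboratory results, which suggests that numeric output was expected. SAP 11.2 limits by-time-point summaries to scheduled visits. These are format and data rules; none of them creates a laboratory table.

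**4. Is the omission declared?** SAP 13 has no row on laboratory summaries. Its note says that only grammatical and typographical changes are left out of the table, so a dropped class of output should have been there.

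**5. Urine protein.** Urinalysis appears among the category tables ("Shift from Baseline of Urinalysis Tests [Parameter" …) but not among the worst-grade tables. It is the one panel of the 6 groups for which this is so.

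- Protocol 1.2 reports for phase I "proteinuria (47.8%, 16 grade 1-2 and 6 grade 3-4". The figure is consistent: 16 + 6 = 22 subjects of 46, and 22/46 = 47.8%.
- Protocol 1.2 also lists proteinuria among the most common adverse events of the earlier phase III study.
- Inclusion criterion 7e allows entry at 1+, and at 2+ or above if the follow-up collection shows less than 2 g in 24 hours. Some subjects can therefore start with an abnormal result.
- For such a subject, a rise from 1+ to 3+ shows in the SAP 8.3 summary only if the label moves from NCS to CS. If both results carry the same label, the table shows no shift.

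**The case against.** **The values are not lost.** SAP 8.3 lists individual laboratory measurements. A reader might infer that within-category drifts can never be seen, and that is wrong. They are in the listing, but they are not summarised or set out by arm.

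**Shift tables might count as change-from-baseline tables.** The synopsis sentence also covers ECOG score, which SAP 8.5.4 delivers as a shift table. This does not rescue the laboratory plan. The synopsis names grade shifts as a further output, and Protocol 8.3.7 asks for means, medians and SDs of continuous laboratory values.

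**Proteinuria is covered elsewhere.** This is largely fair. The phase I rate is an adverse-reaction rate. Clinically significant test findings are adverse events, and SAP 8.2.2 tabulates those by worst grade in each arm. The urinalysis display has three levels, so a reader who infers that urine protein is reduced to normal or abnormal goes too far. What stands is that the laboratory summary depends on the clinical-significance call and does not use the recorded scale.

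**The mock-up tables are not shown.** SAP Appendix 1.1 could contain a numeric laboratory table. SAP 8.3, which lists its tables by name, does not mention one.

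**A loss of statistical power cannot be claimed.** It is tempting to compare the power of a between-arm test on categories with one on measured values. Neither document plans a between-arm test of laboratory data. McNemar's and Bowker's tests assess shift from baseline, and the protocol promises descriptive tables. Any such figure would also need an assumed proportion of abnormal values, which the documents do not give.

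**Conclusion.** The point holds as an undeclared departure from the protocol in descriptive safety output. As SAP 8.3 is written, there are 16 categorical laboratory tables and none of values or change, against two protocol statements that promise numeric summaries. The explicit change-from-baseline commitment is in the synopsis; Protocol 8.3.7 commits to descriptive statistics without those words.

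The consequence is limited. No confirmatory test is affected, the data are collected, and individual results are listed. What is missing is a by-arm numeric summary in a placebo-controlled trial and a graded or ordinal laboratory table for urine protein.

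A reader might also infer that nearly all subjects begin in the lowest category, so that the tables are almost blind. The documents do not support this: inclusion criterion 7 admits hemoglobin from 9.0 g/dL, and AST and ALT up to 3 times the upper limit (5 times with liver metastasis). No baseline distribution is given.

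The conclusion rests on the text of SAP 8.3 and assumes that the unseen mock-up tables add no numeric laboratory table.

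**What to change.** In SAP 8.3:

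1. For each quantitative hematology, chemistry and coagulation parameter, add descriptive statistics of the observed value and the change from baseline, by scheduled visit and arm, on the model of SAP 8.5.1.
2. Add a by-arm table of urine protein from baseline to worst post-baseline result, on the recorded ordinal scale or by CTC grade. This goes a little beyond the protocol's wording but follows from the drug's known profile.

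If the sponsor does mean to drop the protocol's numeric output, SAP 13 should say so and give the reason.

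A baseline-adjusted difference between arms with a confidence interval could be added, but it is optional: the protocol does not promise it, and restoring the protocol's output does not need it.

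The cost is SAP wording, a standard table template and a few more safety tables. No new data and no protocol amendment are needed.
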